2. PROTECTION AGAINST RISKS

- Risk of loss of confidentiality: To protect participant confidentiality, participant information will be kept in their private medical chart or in records maintained by the investigators. Such records will be kept in locked cabinets or password-protected computer files in locked rooms. Participants will not be identified by name in any data presentation.
- Risk of falls and resultant injuries during neurological evaluations. We will provide sufficient physical support to prevent falls during study visits.
- Risks associated with venipuncture: Pressure application and sterile techniques are effective ways to reduce hemorrhage and infection. If the participant feels lightheaded or dizzy, venipuncture will be halted.
- Risks for complications of spinal tap (optional): LP procedure will be performed using good standard technique, under the guidance of clinical site PIs. Study personnel will monitor the volunteer and assess vital signs before and after the LP. Risk of headache will be reduced by using a small diameter atraumatic needle, replacing the stylet before the needle is withdrawn, and inserting the spinal needle with proper orientation. Risk of infection will be minimized by proper sterile technique and never passing through overlying tissue which could be infected. Risk of avulsion of nerve root will be minimized by conscientious technique and listening to the volunteer's report of symptoms during the procedure. Risk of bleeding into the spinal canal will be minimized by taking a history concerning coagulopathies, performing blood coagulation studies when indicated, and not performing LP on patients, who have abnormal results. Risk of brain herniation syndromes will be prevented by evaluating for papilledema and CT scanning for mass lesions, when indicated. Moreover, no LPs will be performed on any participant for whom it is in any way deemed a high risk.
- Risk of claustrophobia: Participants will be screened for claustrophobia prior to the scan, and if claustrophobia occurs during the scan, it will be discontinued immediately.
- Risks associated with the 3T scanners: Participants will be closely screened for contraindications to MRI scanning, and to prevent injury, routine safety procedures will be followed closely, prior to the participant entering the scanner area. If a participant should become anxious during the scanning procedure, due to feelings of claustrophobia, the scanning will be immediately stopped. Investigators can communicate via intercom with participants, while they are being scanned. A number of steps are taken to protect against potential risk, in addition to keeping time-varying magnetic fields (dB/dt), radio frequency (RF) power deposition, and acoustic noise within FDA guidelines. During each study, the participants are continuously monitored visually and can communicate with the researcher at all times. They can immediately be removed from the scanner, if needed. RF power deposition is monitored with software and hardware protection systems and kept below the FDA-approved limit. Acoustic noise is reduced by 12 dB, using a shield placed inside the gradient, using acoustic foam padding, and using specialty ear plugs (Howard Leight Industries, San Diego, CA), which are able to reduce the acoustic noise by 33 dB. To minimize any

discomfort, the participant will be moved inside the scanner at a very slow speed. Furthermore, we will continue to monitor any discomfort, by administering exit questionnaires to all participants. While inside the scanner, participants will have access to a "panic" alarm, which notifies the investigators of a problem and the desire to immediately stop the study. If a participant employs this alarm, they will be immediately taken out of the scanner and any problems will be addressed.

Data and Safety Monitoring Plan

This is not an interventional treatment trial. However, as standard practice for clinical studies in our centers, a detailed data and safety monitoring plan will be developed. Site investigators or coordinators will report all adverse events associated with clinical evaluations, venipuncture, LP, and MRI/MRS procedures to the HMRICC ([name], Director) at HMRI. Serious adverse events will be reported to the HMRICC and IRB within 24 hours, and the HMRICC will immediately notify the Steering Committee members and NINDS officials. The HMRICC and the Steering Committee will ensure that all necessary medical measures are taken to circumvent the adverse event. The Steering Committee will implement measures to prevent the recurrence of similar problems. The Steering Committee will perform quality control on all incoming data reported by the Director of the HMRICC. The Committee will document protocol deviations and violations, and reconcile incomplete or inconsistent data and errors. The Committee will also decide on corrective actions to prevent or minimize further occurrences of such problems. All protocol deviations, adverse events and serious adverse events will be reported to the Data and Safety Monitoring Committee. [name], PhD (University of Pennsylvania), [name] (Mayo Clinic, Jacksonville) and [name] (Mayo Clinic, Arizona) serve as members of the Data Safety Monitoring Committee.

Protocol Deviations

Any protocol deviation as relates to study procedures must be recorded and reported to the HMRICC at the earliest possible time. Some events that can be classified as protocol deviations include but are not limited to the following:

- When one or more of the clinical outcome measures was not completed
- Study visits completed outside of window (+/- 4 weeks from anniversary of baseline visit)*
- COA completed by rater without appropriate and documented training

Additionally the following events will be recorded as irregularities during quality checks by HMRICC:

- SARA rated by multiple raters for the same patient
- Imaging visit completed outside (+/-) 2 week window of clinic visit.*

*If delays were caused as a result of the COVID-19 pandemic, study visits may be completed outside of window following the guidelines described in the study visit section.

3. POTENTIAL BENEFITS OF THE PROPOSED RESEARCH TO THE PARTICIPANTS AND OTHERS

There will be no financial or immediate health benefits for our participants. However, information obtained from this study is expected to improve patient care through better assessment of disease progression or treatment in the future. The risks of participation are clearly defined for our participants and every effort has been taken to minimize their risk. We believe that the risks of participation are greatly outweighed by the benefits to be gained for others.

4. IMPORTANCE OF KNOWLEDGE TO BE GAINED

We believe that the information gained in this investigation will be important in establishing sufficiently large cohorts for clinical trials, developing robust disease progression markers to monitor treatment effects, and identifying the feasible clinical trial designs for disease-modifying drugs to treat SCA1 and SCA3. We believe that the insights gained from this project will ultimately have a significant impact on reducing the morbidity and early mortality associated with these diseases, and such insights may well be applicable to other neurodegenerative disorders. Given the enormous personal and public health burden of neurodegenerative diseases, we believe the limited risks our participants will be asked to incur are significantly outweighed by the new knowledge gained.

Notification of Significant New Findings

Personnel in the MR center maintain a list of the names and contact information of all participants included in research at the MR facilities. This information is required and will be used to notify participants of significant new information about the effects of MR on human health that develop over the course of MR research. Participant's identifying information is stored securely, and it is maintained in a confidential manner by persons with oversight of research conducted at the MR center.

Study Costs/Compensation

The study participant will not be responsible for the cost of any study procedure.

Compensation will be provided to participants who undergo the spinal tap procedure. Participants will be compensated \$100 after CSF is collected, or for unsuccessful CSF collection, if LP needle penetrates the skin.

\$50 compensation will also be provided to participants for completed MR scan visits.

Research Related Injury

In the event that this research activity results in an injury, treatment will be available, including first aid, emergency treatment, and follow-up care as needed. Care for such injuries will be billed in the ordinary manner to the study participant or his/her insurance company. If the participant thinks that he/she has suffered a research related injury, the participant should immediately notify the study staff. The research staff should take timely actions to minimize and treat the injury.

Incidental Findings on MRI

The images or pictures created during this study are for research purposes only and are not intended to provide health care to the participant. However, if the study participant is a control participant, and if the results from the MR show aberrations in the images, a Radiologist, trained in analyzing MR images, will assess the images. The images will not contain any information that leads to the participant's identity. There will be no financial charge to the participant for having the Radiologist assess the images. The investigator for this study will contact the participant, if the recommendation is to further investigate the unusual results of the pictures. However, further medical follow up is not a part of this study, and the study does not have funds set aside for this purpose. Therefore, if the results do show something unusual, any medical follow up cost will be the participant's responsibility and/or the responsibility of the health insurance carrier.

Confidentiality

The records of this study will be kept private. In any publications or presentations, we will not include any information that will make it possible to identify study participants. The record for the study may, however, be reviewed by the research staff directly involved in the study, or by departments at individual sites, with appropriate regulatory oversight. The information from the study will not be entered into the participant's permanent medical record. However, confidentiality is not absolute. Study data will be encrypted, according to current individual site policies for protection of confidentiality. The risks to the participant and his/her family from genetic research are very low. DNA samples will be identified only with a study code. In the event of an unexpected breach of confidentiality, the Genetic Information Non-Discrimination Act (GINA) will help protect the participant from health insurance or employment discrimination based on genetic information. However, GINA will not regulate life or disability insurance.

Protected Health Information (PHI)

PHI created or received for the purposes of this study is protected under the federal regulation known as HIPAA.

Voluntary Nature of the Study

Participation in this study is entirely voluntary. The study participant may choose not to be a part of this study or may withdraw from the study at any time, without affecting the relationship with the participant's physician or other medical staff.

Use of Data and/or Samples

At any time during the study, the participant may revoke authorization to use data and/or samples. However, the sponsor and the study investigator can still keep and use any information that is already received to the extent necessary to preserve the integrity of the research study.

Sample Size Justification

For Aim 1 study of prospective data collection the sample size is guided by feasibility (regarding our realistic ability to enroll premanifest and very early stage subjects across US and Europe), rather than power. The sample size of 200 participants will ensure enrollment of >60 participants with SCA1 and >100 participants with SCA3, which should provide sufficient power at least equivalent to the previous US and EUROSCA studies.

For Aim 2 the sample size is determined based on the RISCA study, which included imaging data from 26 SCA1 mutation carriers and 9 SCA3 mutation carriers and reported significant VBM alterations in SCA1 and trends in SCA3. Based on these data, a Wilcoxon rank sum test will have 95% power to show a difference between controls (mean=0.018, SD=0.019) and SCA (mean= 0.016, SD=0.0019) with 30 subjects per group ($\alpha=0.025$ to take into account the two comparisons of SCA1 and SCA3 versus controls, two-tailed test). Note that this power computation is conservative since the RISCA study included only at-risk subjects, whereas the current study will include both premanifest and early manifest participants. In addition, based on our MRS preliminary data, a Wilcoxon-Mann-Whitney test will have 94% power to show a difference in NAA at baseline between premanifest subjects who have disease onset within the 5 years of the READISCA (conservatively estimated at 1/3 of the participants i.e. $n=7$, mean = 1.2) and those participants who remain in the premanifest stage ($n=14$, mean = 2) for the SCA1 group (standard deviation of 0.4, $\alpha=0.05$, two-tailed test). We will recruit a larger sample size for the SCA3 cohort because: 1) imaging alterations did not reach significance for SCA3 mutation carriers in the RISCA study; 2) the diffusion MRI abnormalities were less pronounced in SCA3 than those in SCA1; and 3) SCA3 is the most common SCA, enabling recruitment of a larger cohort.

Statistical Methods

For Aim 1 data from the participating centers will include demographics, repeat length (expanded and normal alleles), and scores from the SARA, timed measures, patient-reported outcomes (PRO), and health-related quality of life (QoL) for “core ataxia COA”. Range, scale, and outliers of the combined data will be evaluated. Sex will be considered as a biological variable in all statistical analyses. The cluster structure of combined cross-sectional data will be assessed using a variety of non-linear manifold learning methods to identify similarities and dissimilarities. Association and equality of means will be evaluated using parametric and non-parametric inferential hypothesis testing. Longitudinal analyses for repeated measures will be performed using mixed models and generalized estimating equations (GEE regression). As the drop out processes could differ between cohorts the models will take into account the process (pattern mixture models or joint model if necessary).

Propensity Matching: *Post hoc* group comparative analysis will include propensity matching of SCA1/SCA3 subjects from US and those from Europe which have similar covariate profiles, in order to minimize confounding from covariates. Separate logistic regression runs will be performed to obtain the logit for each subject, where the dependent variable is the group (US cohort vs. European cohort) and covariates are nuisance factors such as gender, age, medical history, etc. Histograms of the fitted logit will be constructed for each group, and subjects will be randomly drawn from the same bins within the two histograms. This approach will be bootstrapped so that repeated sampling of the two groups of subjects with similar confounder profiles can be employed during modeling.

For Aim 2 centralized data analysis will be performed. De-identified MRI and MRS data will be analyzed in a blind fashion at UMN, as described previously for volumetric, VBM and MRS analyses. Diffusion MRI data will be analyzed using tract-based spatial statistics (TBSS), which is part of the FMRIB’s Software Library (FSL), and tractography to delineate particular white matter (WM) pathways (e.g., cerebellar peduncles). Functional (rs fMRI) data will be pre-processed using FSL, followed by between-group analyses using seed-based connectivity analysis for particular regions of interest, and independent component analysis/dual regression (MELODIC/FIX) for resting-state networks (RSNs). Normative data from the Human Connectome Lifespan project will supplement matched-control data acquired prospectively. Outcome measures will consist of cerebellar and brainstem volumes, gray matter (GM), and WM loss metrics from VBM, metabolite concentrations, fractional anisotropy, mean diffusivity, radial and axial diffusivity, as well as degree of co-activation within RSNs of interest (e.g., motor function). These multi-modal imaging data will then be incorporated in the predictive model to stratify future clinical trial cohorts in Aim 3.

To compare the imaging biomarkers between SCA1, SCA3 and control cohorts, globally and in a pairwise fashion, we will use Wilcoxon rank sum test. In addition, premanifest carriers and early-stage participants will be compared using Wilcoxon rank sum test. Within each SCA group, premanifest and manifest patients will be compared regarding the biomarkers at baseline and during follow-up. If this approach is not conclusive, cluster approaches will be carried out. Sex will be considered as a biological variable to assess potential sex-based differences in imaging results. Finally, the MR biomarkers will be included in the predictive model (Aim 3).

Ethical Conduct of the Study:

This study will be conducted with the highest respect for the individual participants (i.e., subjects) according to the protocol, the ethical principles that have their origin in the Declaration of Helsinki (18th World Medical Assembly, 1964) and its last revision (Fortaleza, October 2013) (48), the ICH Harmonized Tripartite Guideline for GCP and local laws and regulations of the country where the study is performed.

Clinical Trial Registration:

In order to ensure that information on READISCA reaches the public in a timely manner and to comply with applicable laws, regulations and guidance, HMRICC will be the record owner on ClinicalTrials.gov. HMRI contact information along with participating sites and recruiting status will be registered and available for public viewing.

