* We expect approximately 50% of these subjects will be tested negative for SCA1 and SCA3, and they will serve as controls. If we do not have 30 control subjects, we will recruit additional asymptomatic subjects who are of either sex aged 18 to 65 with neither SCA1 nor SCA3 mutations to serve as additional controls. Exclusion criteria described above also applies to control subjects.

Introduction

Background and study rationale

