We plan to enroll a total of 200 subjects, including 60 early-stage patients (SARA total score 3-9.5), 60 premanifest gene mutation carriers (SARA total score 0-2.5), 60 50%-at-risk subjects (SARA total score 0-2.5), and 20 patients, who had a SARA total score <10 during the previous (2009-2012) natural history study. Confirmatory genotyping for SCA1 and SCA3 will be performed on blood samples obtained at the baseline visit. For 50%-at-risk subjects, genotyping results will be released to the subject's designated physician or genetic counselor after a release of information form has been signed. We strongly recommend genetic counseling for the disclosure of DNA results. We expect that the SCA1-to-SCA3 enrollment ratio will be approximately 1 to 2 in the US and 1 to 1.2 in Europe, based on the previous studies. We anticipate <5%-attrition rate and plan to replace subjects, who drop out, with new subjects. The low attrition rate is expected because study subjects have mild or no disability and low mortality. During the study, there will be individuals who will phenoconvert and some subjects who will want to know the DNA testing results. Subjects who become clinically ataxic will be categorized in the phenoconversion group. Asymptomatic subjects, who receive positive DNA results, will be included in the premanifest carrier group. Prospective data will be categorized at the end of the study into five groups: (1) premanifest carriers whose SARA total score remain in the 0-2.5 range; (2) mildly affected early-stage patients who had an initial SARA total score 3-9.5, which may increase in subsequent years; (3) premanifest participants who phenoconvert during the study period with a SARA total score increase from the 0-2.5 range to ≥ 3 ; (4) SCA1 and SCA3 patients who had a SARA total score <10 during the 2009-2012 CRC-SCA natural history study (or during the ESMI, SPATAX or EUROSCA studies) who may have higher SARA scores during this study; and (5) gene mutation negative controls. Their annual disease progression will be characterized by statistical analyses of annual changes of COA measures, with the SARA total score as the primary outcome measure.

Study duration: Five years

Recruitment of prospective study subjects:

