We will enroll a subset of the prospectively enrolled 200 subjects in Aim 1. These subjects will consist of 30 (20 premanifest and 10 early-phase) subjects with the SCA1 mutation, 40 (27 premanifest and 13 early-phase) subjects with the SCA3 mutation and 30 controls (drawn from at-risk subjects who test negative for SCA1 or

SCA3 gene mutations and from spouses and other relatives who do not have symptoms, signs or risks of ataxia). We will enrich the SCA1 and SCA3 cohorts by inviting participants with a predicted time to ataxia onset within 10 years, based on their CAG repeat length and current age. For premanifest carriers and participants who are 50%-at-risk, we will target an age range of 27-50 years to minimize the probability of including participants too far from disease onset and those who are highly unlikely to have an expansion of CAG repeats in SCA1 or SCA3.

Study duration:

Participants will be scanned (within ± 2 weeks of the clinical study visit) at baseline, 6 month, 12 month, 24 month and 36 month time points during the READISCA study period. All MR visits will include completion of SARA exam prior to MR scan. Three additional time points may be included in the MR sub study to incorporate scans at 6 months, 18 months and 36 months.

Inclusion and exclusion criteria:

Inclusion criteria for Aim 2 will be the same as those in **Aim 1** and willingness to undergo MR procedures.

Exclusion criteria for Aim 2 will be the same as those in **Aim 1** and inability to undergo MRI scanning (claustrophobia, presence of paramagnetic substances or pacemakers in body, weight over 300 lbs.), pregnancy or lactation in women of childbearing potential not protected by an effective means of contraception, and other neurological diseases than those of interest. In addition, potential study participants will be excluded from the study if any of the following criteria are present at any point in the study: structural abnormalities such as subdural hematoma, primary or metastatic intracranial neoplasms, and concurrent illnesses or treatments interfering with cognitive function, such as a stroke or normal pressure hydrocephalus.

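### The Aim 1 sample size is said to assure more than 60 SCA1 and more than 100 SCA3 participants, but the planned 200 include only about 170 expected carriers and nothing in the protocol secures both counts

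*Protocol*

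**What the plan says.** Four places in the Protocol bear on this.

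- **Sample Size Justification, Aim 1.** The size is set by feasibility rather than power. The text then says that 200 participants "will ensure enrollment of >60 participants with SCA1 and >100 participants with SCA3", and that this should give power at least equal to that of the previous US and EUROSCA studies.
- **Prospective Data Collection, Study population.** The 200 are made up of four groups: early-stage disease (60), known carriers who are still premanifest (60), people at 50% risk whose genotype is unknown at entry (60), and a fourth group described as "20 patients, who had a SARA total score <10 during the previous (2009-2012) natural history study".
- **Summary, footnote on the at-risk group.** "We expect approximately 50% of these subjects will be tested negative for SCA1 and SCA3, and they will serve as controls". If fewer than 30 controls result, more will be recruited.
- **Study population, expected genotype mix.** The expectation is that "the SCA1-to-SCA3 enrollment ratio will be approximately 1 to 2 in the US and 1 to 1.2 in Europe".

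The protocol gives no US/Europe split of the 200 and no SCA1 or SCA3 enrolment target for Aim 1. The genotype numbers under Aim 2 apply to the imaging subset only.

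**The concern.** The two targets together require at least 61 + 101 = 162 mutation carriers. That leaves ample room if all 200 participants carry a mutation, but little once the protocol's own controls are taken out. A floor described as assured should follow from the group sizes or from a recruitment rule. Here it depends on an unstated regional split and on how the genotypes happen to fall.

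The consequence is limited but real. The genotype counts are the only support given for the statement about sufficient power in Aim 1. If they are expectations that may or may not be reached, the power statement has the same status.

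**Working it through.** **Inputs from the protocol.** Group sizes 60, 60, 60 and 20. About 50% of the at-risk group mutation-negative. SCA1:SCA3 of 1:2 in the US (SCA1 share 1/3 = 0.333) and 1:1.2 in Europe (SCA1 share 1/2.2 = 0.4545).

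**Assumptions.** The European share *e* of carriers is not given, so it is varied from 0 to 100%. All 60 early-stage patients are counted as carriers, which favours the protocol because the Inclusion Criteria table also admits them on a relative's diagnosis. For the probabilities, genotype within region is treated as an independent draw at the stated ratio.

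**Step 1. The stated counts if all 200 were carriers.**
- All US: 200/3 = 66.7 SCA1 and 133.3 SCA3.
- All Europe: 200/2.2 = 90.9 SCA1 and 109.1 SCA3.

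Both targets hold in expectation at every split, and the chance of meeting both is 0.82 to 0.996. On this count the claim is nearly right.

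**Step 2. Expected carriers under the planned composition.**

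60 + 60 + 20 + 0.5 × 60 = 170.

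More than 60 SCA1 means at least 61. More than 100 SCA3 means at least 101, so SCA1 can be at most 170 − 101 = 69. Both targets hold only for SCA1 from 61 to 69, nine possible values.

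**Step 3. Expected counts with 170 carriers.**

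E(SCA1) = 170 × [(1 − e)/3 + e/2.2] = 56.7 + 20.6e, and E(SCA3) = 170 − E(SCA1).

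- SCA1 above 60 needs e > (60 − 56.67)/20.61 = 0.162.
- SCA3 above 100 needs e < (70 − 56.67)/20.61 = 0.647.

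In whole percentages, both targets are met in expectation for European shares of 17% to 64%.

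**Step 4. Chance of meeting both with 170 carriers.** SCA1 is the sum of Binomial(n_US, 1/3) and Binomial(n_Europe, 1/2.2). The probability is that this sum lies in 61 to 69.

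| European share | E(SCA1) | E(SCA3) | P(both), 170 carriers | P(both), 200 carriers |
|---|---|---|---|---|
| 0% | 56.7 | 113.3 | 0.25 | 0.82 |
| 20% | 60.8 | 109.2 | 0.43 | 0.95 |
| 40% | 64.9 | 105.1 | 0.53 (maximum) | 0.99 |
| 50% | 67.0 | 103.0 | 0.50 | 0.995 |
| 60% | 69.0 | 101.0 | 0.44 | 0.995 |
| 80% | 73.2 | 96.8 | 0.26 | 0.97 |
| 100% | 77.3 | 92.7 | 0.11 | 0.89 |

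**Step 5. Sensitivity.**
- *Random number of at-risk carriers.* With carriers = 140 + Binomial(60, 0.5), the maximum is 0.505. The chance of having at least 162 carriers at all is 0.986, so the limiting factor is mainly the genotype mix.
- *Looser targets.* Reading them as at least 60 and at least 100 raises the maximum to 0.62.
- *All enrolments in Table 3.* 170 + 38 + 11 + 10 + 9 = 238. At the same mix, 238 × 170/200 = 202.3 carriers. With 202 carriers the chance of meeting both is 0.85 to 0.997.

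**The case against.** The strongest reply is that the planned counts are consistent. At 40% European enrolment, 170 carriers give about 65 SCA1 and 105 SCA3, both above target with the controls already removed. No sum in the protocol is wrong. This stands, and a reader who inferred that the targets are out of reach, or that the authors forgot the controls, would be going further than the text allows.

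Second, the probabilities assume that nobody manages the mix. The disease type is usually known in the subject or a first-degree relative before enrolment, and recruitment runs through clinics and registries. Since 162 is below 170, a genotype target could secure both counts. This also stands: the figure of about one half is conditional on unmanaged recruitment. But the protocol states no such target. Meeting both exactly is also a strict test. Under the same model at 40% to 50% European enrolment, the chance of at least 58 SCA1 and at least 96 SCA3 is about 0.82.

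Third, drop-outs are replaced, and the 238 enrolments in Table 3 would usually meet both targets. That softens the point without answering it. The sentence names 200, and late entrants contribute little follow-up: the nine enrolled in Year 5 have a single visit.

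A reader might also infer that 170 is too high, because at-risk people still unaffected at entry are somewhat less likely than 50% to carry the mutation. The direction is sound, but the documents give no figure for the reduction, so none is used here. The Aim 2 sentence about people unlikely to carry an expansion does not supply one, since it describes those whom the age range is meant to keep out.

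**Conclusion.** The assurance does not follow from the design. With about 170 expected carriers, both genotype targets are met in expectation only for a European share of about 17% to 64%. With an unmanaged mix they are met together with probability at most about 0.53, falling to 0.25 if all are from the US and 0.11 if all are from Europe. These figures rest on the protocol's 50% carrier share and regional ratios. The regional split is unknown and was scanned.

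The severity is minor. The size is openly feasibility-based, and no analysis or decision rule depends on the exact counts. Even at the extremes the shortfall is small: 57 instead of 61 SCA1, or 93 instead of 101 SCA3, would raise a standard error by about 3% (√(61/57) = 1.03) or 4% (√(101/93) = 1.04).

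Two stronger conclusions are not supported. One is that the study will be less powerful than its predecessors: the documents do not give comparable sizes for those studies' cohorts, so this cannot be shown. The other is that the protocol overstates the precision of genotype-specific progression rates: it claims none.

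**What to change.** In the Sample Size Justification for Aim 1, do one of the following.

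- Replace the assurance with expected counts: about 170 carriers among the 200, with SCA1 and SCA3 ranges by US/European share (57/113 if all US, 65/105 at 40% European, 77/93 if all Europe).
- State a genotype target for enrolment. At least 61 SCA1 and 101 SCA3 fits within 170 carriers, with a margin of eight.

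In either case, base the power statement on those counts. If replacements are meant to count towards the genotype totals, say so and give the cumulative number instead of 200.

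The first option is a wording change only. The second adds monitoring of genotype during recruitment and may slow filling of the last places.
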